6.2. Timing of Analyses

The final analysis will be performed after database lock when all subjects have been followed through Visit 4, the final study visit, at Day 85-91.

6.3. Analysis Populations

Safety Population: This analysis population includes all randomized participants who received at least one dose of study treatment. Participants with any evidence of dosing according to the memory aid or study IP packaging return will be included in the Safety population.

Modified Intent-to-Treat (mITT) Population: This analysis population includes all randomized participants who are evaluable (see below). If a participant was enrolled more than once, (participants are allowed to be re-enrolled under PI's discretion for scenarios such as, the first enrollment terminated due to the COVID-19 shelter in place order or became ineligible after enrollment.) only the set of data from the most recent enrollment will be included in the mITT population.

The mITT population will be used as the primary efficacy analysis population.

Per-Protocol (PP) Population: This analysis population includes all randomized participants who are evaluable, complied with the assigned IP (see section 4.4.8), and returned to the study site for the TOC visit within the specified window (Visit 4 [Window: Day 85-91]) or were followed up to their diagnosis of recurrent BV. Participants who violated any inclusion/exclusion criterion at any point during the study or engaged in receptive oral, anal, or vaginal sexual intercourse within 24 hours prior to a study visit will be excluded from the PP population. If a participant was enrolled more than once, (participants are allowed to be re-enrolled under PI's discretion for scenarios such as, the first enrollment terminated due to the COVID-19

shelter in place order or became ineligible after enrollment.) only the set of data from the most recent enrollment will be included in the PP population.

In the unlikely event of an error in randomization or IP administration (i.e., incorrect treatment), participants will be grouped by the treatment they actually received in safety analyses but will be grouped by their intended randomized assignment in efficacy analyses.

Evaluable is defined as follows:

- Negative STI tests taken at baseline (*C. trachomatis*, *N. gonorrhoeae*, or *T. vaginalis*);
- For participants 21 years of age or older, documentation of or self-report of a normal or ASCUS HPV negative Pap test prior to screening, or a Pap smear performed at screening/enrollment with normal result

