## **5        SELECTION OF PARTICIPANTS AND STUDY ENROLLMENT AND WITHDRAWAL**

This study will screen approximately 600 women 18-55 years of age who have recurrent RBV, defined as a current BV infection and at least two previous episodes of BV by documentation or self-report in the past year. Women who meet Screening eligibility will be treated with a standard course of oral metronidazole or another CDC-recommended BV treatment. Participants will return within approximately one week of completing the metronidazole treatment or other CDC-recommended BV treatment, for assessment of clinical cure. Clinical cure of BV is defined as  $\leq 2$  of 4 Amsel criteria and absence of reported symptoms of BV (i.e. no malodorous discharge consistent with BV).

Participants who return for the Enrollment Visit, V1 and are determined to be clinically cured will be offered to review and sign the Enrollment consent. Participants who consent and meet Enrollment eligibility will be randomized in a 1:1 ratio to twice weekly blinded suppressive therapy with TOL-463 or placebo. It is estimated that approximately 250 participants will be eligible for Enrollment with approximately 125 participants in each suppressive therapy group.

No exemptions will be granted on Screening or Enrollment eligibility criteria for this DMID-sponsored trial.

Participants will be recruited from health clinics in the U.S.

Those participants who enroll in the study will undergo up to 3 scheduled Follow-up visits to evaluate clinical diagnosis of BV at each visit. Participants who develop vaginal symptoms between scheduled visits will be asked to return for an unscheduled visit. If at any time during a follow-up visit a participant is diagnosed with clinical BV ( $> 2$  Amsel criteria), the study endpoint of BV reoccurrence is met, and participation in the study will end.

The study will target a total of 200 evaluable participants.

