## 10 STATISTICAL CONSIDERATIONS

### 10.1 Study Hypotheses

The primary objective of the study is to evaluate the clinical efficacy of a twice-weekly application of the TOL-463 vaginal insert for the suppression of BV following successful induction with oral metronidazole or other CDC-recommended BV treatment in women with a history of recurrent BV. Clinical efficacy (suppression) is defined by clinical cure (see [Section 3.3.1](#)). There is one planned hypothesis test with respect to the primary outcome measure. The hypothesis test compares the proportion of participants with recurrent BV by V4 between treatment arms. The null hypothesis for the comparison is that there is no difference in cure rates between treatments, with a two-sided alternative. The test will be conducted using the Pearson Chi-Square test at the 5% two-sided significance level.

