4.3.2.1. Screening Visit(s) Exclusion Criteria

1. Diagnosis of another vaginal or vulvar condition that may confuse interpretation of response to IP*;

*For example: erosive lichen planus, desquamative inflammatory vaginitis, or contact dermatitis involving the vulvar epithelium.

2. Concurrent VVC infection with inability to be treated with oral fluconazole;
3. Infectious cause of cervicitis (e.g., *N. gonorrhoeae*, *C. trachomatis*, or *T. vaginalis*) confirmed on physical examination and/or with laboratory testing**⁺;

** Women may be rescreened for eligibility following successful treatment of confounding STI.
+Results of NAAT testing will be reviewed prior to enrollment.

4. Active genital lesions, including ulcers or vesicles consistent with herpes or warts;
5. Planned ongoing immunosuppressive therapy or systemic antibiotic treatment during the course of the study;
6. History of hypersensitivity, allergy or other contraindication(s) to metronidazole or other CDC-recommended BV treatment used to treat subject;
7. History of hypersensitivity to any TOL-463 formulation components (see IB for product information);
8. Current or untreated cervical intraepithelial neoplasia (CIN) or cervical carcinoma;
9. Currently pregnant or nursing;
10. Any other condition that, in the opinion of the investigator, would interfere with participation in the study;
11. Previous enrollment in the study or at the investigator's discretion.

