5. SAMPLE SIZE CONSIDERATIONS

Efficacy analyses will be performed in an evaluable subset of the enrolled population; this subset was used to derive the study's sample size. Assuming a 40% BV recurrence rate among women receiving placebo and a 50% reduction in recurrence among women treated with TOL-463 (i.e. 20% recurrence rate among TOL-463 recipients) and a 1:1 allocation ratio between treatment arms, a sample size of 200 evaluable participants will provide at least 85% power using the Chi-Square Test. Assuming 80% of enrolled participants will be evaluable for the primary analysis, the enrollment target is set to a total of 250 participants to achieve 200 evaluable participants.

The study was closed early due to the uncertain future of the study product's manufacture and availability. It was unrelated to the safety and efficacy of the study product. The power of the actual sample size will be provided in the CSR.

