6.5. Missing Data

For primary BV recurrence endpoint:

For the mITT analysis population, the BV status of subjects whose status cannot be determined by the TOC visit (visit 4) for any reason will be considered ‘treatment failure’, including subjects who discontinued early from the study and lack of treatment effect.

For the PP analysis population, subjects whose BV status cannot be determined by the TOC visit for any reason will be excluded from the analysis.

For secondary endpoints, missing values will be further excluded from the mITT and PP populations.

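### Keeping only a repeat woman's latest enrolment drops an evaluable first randomised record from the mITT, and no planned table shows whether that matters

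*SAP*

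**What the plan says.** SAP 6.3 lets the site investigator re-enrol a participant at discretion. It gives two examples, a first enrolment ended by a COVID-19 order and ineligibility found after enrolment, and the list is open. For such a woman "only the set of data from the most recent enrollment will be included in the mITT population". The same rule is written for the per-protocol (PP) population. The mITT is the primary efficacy population.

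SAP 6.5 sets the missing-data rule within the mITT: "subjects whose status cannot be determined by the TOC visit (visit 4) for any reason will be considered" a treatment failure. SAP 4.5.1 says the same of women who withdraw or drop out early.

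Protocol 10.5.1 defines the mITT as all randomised participants who are evaluable and has no rule for repeat enrolment. Protocol 5.2.2 says that women who received product and then left the study are not replaced. SAP 15 states that the SAP's analyses match those in the protocol.

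On eligibility, screening exclusion criterion 11 begins "Previous enrollment in the study" and goes on to add the investigator's discretion as an alternative. Protocol section 5 says "No exemptions will be granted on Screening or Enrollment eligibility criteria for this DMID-sponsored trial". The PP definition in SAP 6.3 removes "Participants who violated any inclusion/exclusion criterion at any point during the study".

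**The concern.** Take two evaluable women whose enrolments are stopped by the same COVID-19 order. The one who stays away is in Table 6 as a failure. The one who returns has that record replaced by whatever happens at her later enrolment. What separates them is a choice by the woman and the investigator, made after randomisation.

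The primary comparison is then not strictly by first randomisation. If returning is related to arm, even indirectly, the two proportions are affected unequally. The rule also departs from the protocol's mITT definition without being declared, so a reader of the report would not know to ask how many records were superseded or in which arm.

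**Working it through.** **The plan's own figure.** Inputs: "The test will be conducted using the Pearson Chi-Square test at the 5% two-sided significance level" (Protocol 10.1); "Assuming a 40% BV recurrence rate among women receiving placebo and a 50% reduction in recurrence among women treated with TOL-463", hence a "20% recurrence rate among TOL-463 recipients) and a 1:1 allocation ratio between treatment arms" (SAP 5); 200 evaluable, so n = 100 per arm. Power = Φ{[d − 1.96·√(2·p̄(1−p̄)/n)] / √[(p₁(1−p₁)+p₂(1−p₂))/n]}. With p₁ = 0.40, p₂ = 0.20, p̄ = 0.30 and d = 0.20:

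- 1.96·√(0.42/100) = 0.127
- √(0.40/100) = 0.0632
- Φ(0.073/0.0632) = Φ(1.154) = 87.6%

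This meets the stated floor of 85%. The enrolment target also reproduces: 200/0.80 = 250.

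**Which first enrolments are affected.** The failure rule in SAP 6.5 works only inside the mITT, so the woman must have been evaluable at the first enrolment.

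| First enrolment ended because of | Evaluable then? | Scored if she does not return | If she re-enrols |
|---|---|---|---|
| COVID-19 order, baseline STI tests negative and Pap acceptable | Yes | Failure | First record dropped |
| Positive baseline STI test or unacceptable Pap | No | Not in mITT | Nothing scored is lost |

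**What the planned outputs show.** Table 7 takes COVID terminations out of the mITT. Returners' first enrolments are already out under SAP 6.3. Table 7 therefore contains no COVID-terminated enrolments, and the uneven scoring of COVID cases disappears there. It does not restore any first randomised record. The mITT exclusion rows of Table 4 cover only the STI and Pap reasons. SAP 9.3 gives a repeat woman a new subject identifier, and no listing pairs her two enrolments.

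**Size, by assumption.** The documents give no count of repeat women. Suppose k superseded first records in an arm of n are put back and scored as failures, in place of outcomes that would have followed the planned rate p. The arm's proportion rises by k(1−p)/n.

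- Five in one arm of 125, if all enrolled were evaluable: TOL-463 5×0.80/125 = 3.2 points; placebo 5×0.60/125 = 2.4 points.
- Five in each arm of 100: TOL-463 0.20×0.95 + 0.05 = 24%; placebo 0.40×0.95 + 0.05 = 43%. The difference is 19 points and power is 81.7%.
- One to ten in each arm of 100: the difference is 20×(1−k/100), from 19.8 to 18.0 points; power runs from 86.5% to 75.4%.
- Five in one arm of 100 only: 24% against 40%, power 68.2%, if all are in TOL-463; 20% against 43%, power 94.4%, if all are in placebo. The shift can go either way.

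**The case against.** Using one prespecified record per woman is a defensible choice. Both named reasons for re-enrolment are unrelated to product response, and participants and site staff are blinded. Scoring a shelter order as treatment failure says little about the product. Table 7 already deals with COVID terminations, and Listings 1 and 3 would show much of the detail by arm. All of this stands. It is why the planned primary analysis need not change and why no bias can be asserted. It does not supply an analysis by first randomisation, and it does not explain why SAP 15 is silent.

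Four stronger readings are tempting, and the documents do not support them.

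- A reader might infer that every re-enrolment erases a failure. It does not where the first enrolment was non-evaluable. An unacceptable screening Pap is a natural route to later ineligibility, since the result is not required before enrolment.
- A reader might infer that the PP population knowingly keeps ineligible women. The text removes anyone who violated a criterion, and the discretion wording in criterion 11 can be read as allowing investigator-approved re-enrolment. This is an ambiguity to settle.
- A reader might take five records of 125 as a 4-point shift (5/125). That assumes all five replaced outcomes would have been non-failures. At the planned rates the shift is 3.2 or 2.4 points.
- A reader might infer that a returning woman is newly randomised, or that her experience of the product drives her return. The documents state neither.

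**Conclusion.** The point holds for women who were evaluable at a first enrolment and later re-enrolled. For them the latest-enrolment rule replaces a randomised record that would otherwise count as failure, on the strength of a discretionary decision after randomisation. The rule is not in the protocol's mITT and is not declared. The uneven scoring of COVID terminations is removed in Table 7, but nothing planned analyses women by first randomisation.

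Neither the number affected nor the direction of any bias can be established. The figures above rest on assumed counts, the planned recurrence rates and the planned arm sizes. SAP 5 reports that the study closed early, so each record may weigh more than shown. With one or two repeat women the effect is small when spread over both arms: at two per arm of 100 the difference is 19.6 points. This is a cheap improvement.

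**What to change.** 1. Add a sensitivity version of Table 6 that uses each evaluable woman's first randomised enrolment under the SAP 6.5 rule. State in a footnote how a woman who was non-evaluable at first and evaluable later is handled; taking the first enrolment at which she is evaluable would fit the mITT definition.
2. Add a row to Table 4 for superseded enrolments, by arm, and a listing that pairs each repeat woman's assignments and outcomes.
3. Declare the latest-enrolment rule in SAP 15 as an addition to the protocol's mITT definition.
4. Separately, reconcile exclusion criterion 11, the no-exemptions statement and the PP re-enrolment sentence, so that it is clear whether investigator-approved re-enrolment counts as a violation.

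The cost is one table, one row, one listing and a few sentences, all from data already held. The drawback is that scoring COVID-terminated first enrolments as failures adds noise, so this analysis belongs beside the planned primary analysis and does not replace it.

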#### **Pelvic Examination:**

During the initial screening visit, V0 pelvic examination, the clinical diagnosis of BV will be based on the presence of 3/4 of the following Amsel criteria:

---

1. Homogenous vaginal discharge characteristic of BV;
2. A fishy odor of the vaginal discharge with the addition of a drop of 10% KOH (positive whiff test);
3. Clue cells  $\geq$  20% of the total vaginal squamous epithelial cells on saline microscopy;
4. Vaginal fluid pH  $>4.5$ .

Instructions for obtaining and determining the presence of Amsel clinical criteria can be found in the protocol-specific MOP.

During the enrollment visit's, V1 pelvic examination, a clinical determination to confirm BV cure following metronidazole or CDC-recommended BV treatment induction will be determined by  $\leq$  2 of 4 Amsel criteria and absence of BV symptoms (defined as absence of homogenous discharge and odor).

At all other follow-up visits on suppressive study IP (V2-V4), a clinical determination of BV recurrence will be determined as  $>$  2 of 4 Amsel criteria by pelvic examination.

For the enrollment V1 or follow-up (V2 – V4) visits, participants will be scheduled outside of menses as soon as possible after cessation of menstruation.

At all follow-up visits (V2-V4), a clinical diagnosis of VVC will be based on vulvovaginal signs (edema, erythema, and excoriation) and symptoms (itching, burning, and irritation) and a positive KOH microscopy with identification of yeast forms (hyphae/pseudohyphae) or budding yeasts. A confirmatory Candida culture with speciation will also be performed; Candida culture in the setting of incomplete criteria for the clinical diagnosis may be obtained at the discretion of the study clinician.

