### 10.5.1 Analysis Populations

Safety Population: This analysis population includes all randomized participants who received at least one dose of study treatment.

Modified Intent-to-Treat (mITT) Population: This analysis population includes all randomized participants who are evaluable.

The mITT population will be used as the primary efficacy analysis population.

Per-Protocol (PP) Population: This analysis population includes all randomized participants who met all inclusion/exclusion criteria throughout the study, are evaluable (defined below), complied with the assigned IP, and returned to the study site for the TOC visit within the specified window (Visit 4 [Window: Day 85-91]) or were followed up to their diagnosis of recurrent BV.

Evaluable is defined as follows:

- Negative STI tests taken at baseline (*C. trachomatis*, *N. gonorrhoeae*, or *T. vaginalis*);
- For participants 21 years of age or older, documentation of or self-report of a normal or ASCUS HPV negative Pap test prior to screening, or a Pap smear performed at screening/enrollment with normal result

A participant is compliant with the study treatment if she misses  $\leq 2$  non-consecutive doses of IP per month, as assessed by participant memory aid and returned IP and packaging at each follow up visit (V2, V3, V4).

In the unlikely event of an error in randomization or IP administration (i.e., incorrect treatment), participants will be grouped by the treatment they actually received in safety analyses but will be grouped by their intended randomized assignment in efficacy analyses.

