8. EFFICACY EVALUATION

8.1. Primary Efficacy Analysis

The primary efficacy endpoint for the final analysis is the proportion of subjects with recurrent BV by Test of Cure (TOC, Visit 4 window: Day 85-91) as defined in section 3.3, and in section 6.5 for missing BV status by TOC.

The number of subjects, the proportion of subjects with RBV up to and including V4 will be presented overall and by treatment group with two-sided 95% Wilson confidence interval (no continuity correction). In addition, the difference in proportions between the TOL-463 Vaginal Insert arm and the Placebo group and 95% Newcombe confidence intervals (based on the Wilson CI for the individual proportions) will be presented. See [Table 6](#).

The pseudocode to fit the above analyses is below:

```
proc freq data=dataset;
  Table treatment*cure /chisq riskdiff(Newcombe) binomial(wilson) out=output
  alpha=.05;
run;
```

The primary efficacy analysis will be performed in the mITT population ([Table 6](#)). As a sensitivity analysis, the primary endpoint will additionally be assessed among all subjects in the mITT population except those terminated early due to study disruptions from the COVID-19 pandemic ([Table 7](#)). Analysis of the primary outcome measure will be repeated in the PP analysis population (secondary analysis of primary outcome). See [Table 8](#).

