Early Discontinuation from Treatment ^d	x	xx	x	xx	x	xx
Early Termination from Study ^b	x	xx	x	xx	x	xx

^a Received Treatment includes subjects who successfully received at least one dose of study treatment. It is unknown whether subjects received at least one dose if they were terminated early before Visit 2 and a Study Product Dispensing assessment at the early termination visit could not be conducted.

^b Completed Follow-up includes subjects who remained BV suppressed and were followed-up through Visit 4 as well as subjects whose participation ended prior to Visit 4 due to a clinical BV diagnosis. Terminated Early includes subjects who terminated from the study early for reasons other than a clinical BV diagnosis.

^c A blinded case review committee reviewed subjects' data to determine treatment compliance throughout the study for each subject.

^d Subjects who discontinued treatment due to RBV are included.

Table 4: Analysis Populations by Treatment Group

Analysis Populations	Reason Subjects Excluded	TOL-463 Vaginal Insert (N=X)		Placebo (N=X)		All Subjects (N=X)	
		n	%	n	%	%	n
Eligible for Safety Analysis Population	N/A	x	xx	x	xx	x	xx
Excluded from Safety Analysis Population	Any Reason	x	xx	x	xx	x	xx
	Did not receive at least one dose of study product	x	xx	x	xx	x	xx
Eligible for Modified Intent-to-Treat Analysis (mITT) Population	N/A	x	xx	x	xx	x	xx
Excluded from for Modified Intent-to-Treat Analysis (mITT) Population	Any Reason	x	xx	x	xx	x	xx
	Positive NAAT test results at baseline for C. trachomatis, N. gonorrhoeae, or T. vaginalis	x	xx	x	xx	x	xx
	HPV Criterion ^a	x	xx	x	xx	x	xx
Eligible for Per-Protocol (PP) Analysis Population	N/A	x	xx	x	xx	x	xx
Excluded from Per-Protocol (PP) Analysis Population	Any Reason	x	xx	x	xx	x	xx
	Did not meet inclusion/exclusion criteria	x	xx	x	xx	x	xx
	Positive NAAT test results at baseline for C. trachomatis, N. gonorrhoeae, or T. vaginalis	x	xx	x	xx	x	xx
	HPV Criterion ^a	x	xx	x	xx	x	xx
	Was not compliant with study product	x	xx	x	xx	x	xx
	Did not return to study site for the TOC visit within the specified window (Visit 4, Day 85-91)	x	xx	x	xx	x	xx
	Was not followed up to the diagnosis of recurrent BV	x	xx	x	xx	x	xx

Notes: N=Number of all enrolled subjects

^a For participants 21 years of age or older, documentation of or self-report of abnormal, or ASCUS HPV Positive Pap test prior to screening, or Pap smear performed at screening/enrollment with abnormal result.

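### The per-protocol rule can drop a BV-free woman seen after Day 91 yet keep a recurrence found the same day, so late Visit 4s would raise PP recurrence

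*SAP*

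**What the plan says.** - **PP membership.** SAP 6.3 requires that a woman be evaluable and compliant, and it takes in those who came back "for the TOC visit within the specified window (Visit 4 [Window: Day 85-91]) or were followed up to their diagnosis of recurrent BV". Protocol 10.5.1 has the same two routes joined by the same conjunction: "returned to the study site for the TOC visit within the specified window (Visit 4 [Window: Day 85-91]) or were followed up to their diagnosis".
- **Missing status in PP.** Under SAP 6.5, "subjects whose BV status cannot be determined by the TOC visit for any reason will be excluded from the analysis".
- **Endpoint.** SAP 8.1 defines it as the "proportion of subjects with recurrent BV by Test of Cure (TOC, Visit 4 window: Day 85-91").
- **Population table.** The Table 4 shell lists as a PP exclusion reason: "Did not return to study site for the TOC visit within the specified window (Visit 4, Day 85-91"). A separate row covers women not followed to a diagnosis of recurrence.
- **Scheduling.** Protocol 7.1 (Pelvic Examination) says of V1 and V2 to V4 that "participants will be scheduled outside of menses as soon as possible after cessation of menstruation". It does not say the visit must stay inside its window. By contrast, the menses note in the V1 exclusion criteria (protocol 5.1.2.2) confines re-evaluation to the enrollment window.
- **Use of PP.** The primary endpoint is repeated in PP (Table 8), as are the person-time rate (Table 10) and the Kaplan-Meier curve (Figure 4). SAP 8.2 calls the PP repeats of the secondary analyses corroborative and sensitivity analyses.

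**The concern.** Membership of an analysis set should not depend on the outcome being analysed. Take two women who took the product as directed and whose Visit 4 fell on Day 95. The one with more than two Amsel criteria was followed to a diagnosis of recurrence and can enter PP by the second route. The one with two or fewer meets neither route and is removed. Yet her clear examination is informative: no recurrence was found in her through the whole Day 85-91 window.

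Removing only event-free women leaves the numerator alone and shrinks the denominator, so the recurrence proportion can only go up. The Table 10 rate moves the same way, because each removed woman takes her full event-free follow-up with her.

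This bears on what PP is for. In mITT, undetermined status counts as treatment failure (SAP 4.5.1 and 6.5), which already pushes recurrence up. PP is the analysis without that imputation, so it should show whether the imputation drives the result. A PP rule that can push the same way makes it a weaker check. The trial also closed early (SAP section 5), so discarding fully followed women costs precision.

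**Working it through.** **Inputs.** Recurrence of 40% on placebo and 20% on TOL-463, 1:1 allocation, and 200 evaluable women, so 100 per arm (SAP section 5, protocol 10.2). Two-sided 5% Pearson chi-square (protocol 10.1). The documents give no late-visit rate. Let *u* be the share of BV-free women whose Visit 4 is after Day 91; values of *u* are assumptions.

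**The plan's own figure.** Power = Φ[(0.20 − 1.96·√(2·0.3·0.7/100)) / √((0.24 + 0.16)/100)] = Φ[(0.20 − 0.127)/0.0632] = 87.6%. An exact calculation gives 88.0%. The stated figure of at least 85% is met, so 40% and 20% are used below.

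**Plain reading: late recurrers kept, late BV-free women dropped.** With true recurrence *p*,

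p_PP = p / [p + (1 − p)(1 − u)].

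| u (assumed) | Placebo | TOL-463 | Difference | Risk ratio |
|---|---|---|---|---|
| 0 | 40/100 = 40.0% | 20/100 = 20.0% | 20.0 points | 0.50 |
| 10% | 40/94 = 42.6% | 20/92 = 21.7% | 20.8 points | 0.51 |
| 15% | 40/91 = 44.0% | 20/88 = 22.7% | 21.2 points | 0.52 |
| 20% | 40/88 = 45.5% | 20/84 = 23.8% | 21.6 points | 0.52 |

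**Odds ratio.** The PP odds are p / [(1 − p)(1 − u)], so OR_PP = OR × (1 − u_placebo)/(1 − u_TOL). With equal lateness the factor is 1 and the odds ratio stays at (0.20/0.80)/(0.40/0.60) = 0.375.

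**Chi-square with equal lateness.** It falls slightly, from 9.52 (u = 0) to 9.22 (u = 10%) and 8.86 (u = 20%).

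**Unequal lateness (illustration only).**
- 20% late on placebo and 10% on TOL-463: 45.5% − 21.7% = 23.7 points before rounding of the arms; OR = 0.375 × 0.8/0.9 = 0.333.
- 10% late on placebo and 20% on TOL-463: 42.6% − 23.8% = 18.7 points before rounding of the arms; OR = 0.375 × 0.9/0.8 = 0.422.

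**Alternative reading: late women dropped whatever the result.** Women who recur at V2 or V3 leave the study then and never face the Visit 4 window, so some inflation remains. Assume that half of recurrences are found before Visit 4 (the documents do not say) and that 10% of women reaching Visit 4 are late, regardless of result:
- Placebo: (0.20 + 0.9 × 0.20)/(1 − 0.1 × 0.80) = 0.38/0.92 = 41.3%.
- TOL-463: (0.10 + 0.9 × 0.10)/(1 − 0.1 × 0.90) = 0.19/0.91 = 20.9%.

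If every recurrence were found at Visit 4, this reading would give no inflation.

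**The case against.** **The text does not settle that late recurrers are kept.** SAP 8.1 ties the endpoint to the Day 85-91 window, and the Table 4 row excludes an out-of-window visit without reference to outcome. The follow-to-diagnosis route also has an evident purpose: women who recur early are terminated and can never attend Visit 4. The ambiguity stands. But no passage says that a late recurrer is dropped, and the Table 4 row read alone would also remove women who recurred at V2 or V3, so it has to be read together with the second route. No passage admits the late BV-free woman on either reading.

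**Late visits may be few.** The menses instruction shows that a visit can be moved, not that many pass a seven-day window. This stands. The Table 5 shell provides a row for out-of-window visits, so they are foreseen, but their number is unknown.

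**The comparison hardly moves.** With equal lateness this is right, and no treatment difference is created under the null. A reader might infer that the rule manufactures or exaggerates a benefit. The documents do not support that: nothing in them suggests that lateness differs by arm.

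**The Kaplan-Meier curve may be unaffected.** SAP 4.5.1 and 8.2 allow a woman without recurrence to be censored when she loses eligibility for the analysis population. That suggests her BV-free time up to that point may be retained. A reader might infer that Figure 4 is biased in the same way as Table 8; that depends on how this rule is applied, and the SAP does not say.

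**A visit-window criterion is ordinary for a PP set, and PP is only supportive.** Both true. The defect is that the criterion can act on one outcome only.

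**Conclusion.** On its plain wording the PP rule depends on outcome. If any BV-free woman has a late Visit 4, PP recurrence in her arm is raised in Table 8 and, by the same logic, in Table 10. The direction is arithmetic. The size is conditional: at an assumed 10% to 20% late, about 2.6 to 5.5 points on placebo and 1.7 to 3.8 on TOL-463, with the difference moving 0.8 to 1.6 points and the odds ratio unchanged when lateness is equal.

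It would go too far to say that PP recurrence is inflated in both arms as a fact, since that needs late visits to have occurred in both. It would also go too far to extend the point to the primary result: the mITT definition has no visit-window rule. This is a defect in a supportive analysis, worth correcting because the correction is cheap.

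**What to change.** 1. In SAP 6.3, admit to PP any otherwise eligible woman with a Visit 4 Amsel result on or after Day 85 and up to a stated upper limit, whatever the result. Set the limit before unblinding. Without one, a recurrence found long after the endpoint window would still count as occurring by Visit 4.
2. State how a recurrence first found after Day 91 but within the limit is counted, given SAP 8.1's Day 85-91 wording and the longer time at risk.
3. Change the Table 4 exclusion reason to match.
4. Keep the strict Day 85-91 version as a supplementary PP row.
5. Record the departure from protocol 10.5.1 in SAP section 15, which now says that the analyses coincide with the protocol.

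Dropping late women of both outcomes is not an adequate substitute, because women who recur at V2 or V3 are never exposed to the window.

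The cost is a wording change, one population flag and one extra table row. The downside is that a few visits fall later after the last dose, with slightly longer time at risk. The change does not reach BV-free women last seen before Day 85, who would still be outside PP.
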